### **Payment**

Participants will be compensated \$100 for the baseline assessments and for each of the 3 outcome assessments, for a total of \$400 possible for completing all study assessments. Participants will not be compensated for their participation in the PRE-CARE intervention, only for completion of study assessments.

### **Removal of Participants**

All instances of study drop out will be documented using the Premature Termination form on REDCap, including reason for dropout, who decided the participant would drop out (participant, study staff or PI), and whether the drop out resulted from burden of intervention, study assessment, or another reason. Withdrawn participants will be encouraged to continue to participate in study assessments throughout the 1-year follow-up period in order to optimize the intention-to-treat assessment design. Participants may withdraw voluntarily at any time for any reason. Withdrawn participants will be encouraged to participate in an exit interview to provide feedback on why the intervention did not work for them and suggestions for improvement. Participants may withdraw voluntarily at any time for any reason. Participants

will also be informed during the consent process that information already collected as part of the study will remain in the study record even if they later withdraw. There are two types of participant withdrawal: “intervention withdrawal” and “study withdrawal”.

1. **Intervention withdrawal:** A participant drops out of the PRE-CARE intervention (either because they are no longer interested or because the study PI feels the intervention is no longer appropriate), but still provides the research team with post-intervention data by completing assessments at the follow-up timepoints and exit interview. Intervention withdrawal would be defined as one or more of the following: Family declines to respond to PRE-CARE screening questions; family refuses to engage with the interventionist in a discussion about unmet needs; for family decline to accept the Family Resource Booklet. If a participant responds to screening questions, discusses needs with the interventionist, and accepts the Family Resource Booklet, but declines only the optional resource navigation component of the intervention, this would not constitute an intervention withdrawal.
2. **Study withdrawal:** A participant (or provider on behalf of participant) explicitly communicates that they are no longer interested in being a part of the study at all, including future assessments and compensation. Cases of intervention withdrawal are not automatically considered to be study withdrawal unless the participant specifically states that they never wish to be contacted again by the study, or if the study investigator deems any future contact would be inappropriate.

Participants may be removed if:

1. If the study investigator or treating provider feels the study is negatively impacting the participant’s health or wellbeing resulting in increasing severity of illness that is clinically assessed as such by the study PI. The interventionist and study PI will have weekly meetings/supervision to evaluate study progress, and discuss and address any concerns about participant risk. Any cases of a parent reporting that either their child’s ADHD symptoms or their own parental mental health symptoms are worsening will be assessed clinically and study PI will determine whether the participant should be removed from the study and whether an adverse event or unanticipated problem should be filed.
2. If the participant presents with clinically determined safety risk to self or others.

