### 4.2 Study Outcome Measures

#### 4.2.1 Primary Outcome Measures

**Primary outcomes** include the following clinical outcomes:

- ADHD Symptoms (ADHD-RS-IV Preschool Version)
- Child Psychiatric Symptoms (Child Behavior Checklist 1.5-5)

**Secondary outcomes** include the following measures of unmet social needs, treatment access and utilization, parent activation, parent mental health/stress, adverse childhood experiences, and feasibility/acceptability:

- Unmet Social Needs Outcomes (Children's Health Watch Vital Signs and National Survey of Children's Health pertaining to all unmet needs in the PRECARE Screener).
- Adverse Childhood Experiences (CYW ACE-Q)
- Parental Depression (PHQ-9)
- Parental ADHD (ASRS-v1.1)
- Global Perceived Stress (PSS)
- Parenting Stress (PSI-SF)
- PRE-CARE Feasibility and Acceptability Questionnaire
- Semi-structured in-depth exit interviews with parent/guardians on feasibility/acceptability

**Process outcomes** include the following measures of study and intervention processes:

- **Recruitment and enrollment statistics** (number of parent/guardians referred and from which clinic, contacted, screened, eligible, refused participation, enrolled, dropped out of study or intervention early and why, and completed intervention)
- **Contacts with parent/guardians** (number, frequency, modality, length)
- **Referrals made** (including agencies, date of referral, and parent/guardian vs. staff referral)
- **Resources accessed** (including specific resource accessed, resource category, date accessed)
- **Needs resolved** (date at which a participant indicates they no longer need help with a need and why)

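### A PI removal "from the study" after reported worsening is tied to neither defined withdrawal type, so follow-up may stop because of the outcome

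*Combined protocol and SAP*

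**What the plan says.** All of the text at issue is under Removal of Participants in Section 9.

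- **Two withdrawal types.** After intervention withdrawal, follow-up assessments continue. This type can arise "because the study PI feels the intervention is no longer appropriate". Study withdrawal ends everything, including assessments. It is defined by the participant, or a provider on their behalf, saying so. An intervention withdrawal also becomes a study withdrawal "if the study investigator deems any future contact would be inappropriate".
- **Protection of follow-up.** "Withdrawn participants will be encouraged to continue to participate in study assessments throughout the 1-year follow-up period", with an intention-to-treat aim given as the reason. Also, "information already collected as part of the study will remain in the study record even if they later withdraw".
- **Removal.** The first listed ground is that the investigator or treating provider "feels the study is negatively impacting the participant", with increasing severity confirmed by the PI. Under that ground, reports that the child's ADHD symptoms or "their own parental mental health symptoms are worsening will be assessed clinically", after which the "study PI will determine whether the participant should be removed from the study".

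Section 4.2.1 makes the ADHD-RS-IV Preschool Version a primary outcome, and lists parental depression and stress scales as secondary outcomes. Sections 12.2 and 12.3 say the pilot is to supply within-group SDs and baseline-to-follow-up correlations for powering the next trial. They give no method for missing data.

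**The concern.** The event that prompts a removal decision is deterioration on the trial's own endpoints, and the removal is worded as being from the study rather than from the intervention. Read literally, assessments stop for families chosen because they got worse, which works against the intention-to-treat aim stated a few lines earlier.

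Detection would also differ by arm. PRE-CARE families are offered meetings every two weeks, and interventionists have weekly supervision with the PI (Sections 8 and 9). Study staff do not initiate contact with controls between questionnaires (Section 5). Worsening would be heard mainly in PRE-CARE, so arm-specific SDs and retention, both outputs of the pilot, would not be comparable.

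At stake are the two quantities on which the next trial's sample size will rest.

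**Working it through.** **1. The plan's own figure.** Section 12.2 gives 30 per group, 25% attrition, and a requirement of about 15 per group. 30 × (1 − 0.25) = 22.5, which exceeds 15, so the figure is reproduced. The rule counts how many are lost and says nothing about who is lost. There is no power calculation to check.

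**2. The text side by side.** A PI removal fits neither withdrawal type.
- Study withdrawal is defined by what the participant or provider communicates, with the investigator entering only if contact is judged inappropriate.
- Intervention withdrawal mentions a PI decision in its opening, but its defining list contains only family refusals (of the screener, of the discussion, of the booklet). A control has no PRE-CARE to withdraw from.
- The encouragement to continue cannot sensibly cover study withdrawal as defined, because that already excludes future assessments.

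Staff could read a PI removal either way.

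**3. Size if follow-up does stop.** The documents give no SD, correlation or removal rate. Assumptions: baseline X and follow-up Y are bivariate normal with SD 1 and correlation ρ = 0.6, and exactly the worst fraction q of an arm loses follow-up.

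Cutting off the top q of a standard normal leaves variance v = 1 − zλ − λ², where z is the (1 − q) quantile and λ = φ(z)/(1 − q).
- q = 5%: z = 1.645, λ = 0.1086, v = 0.810
- q = 10%: z = 1.282, λ = 0.1950, v = 0.712

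*Selection by follow-up level:* Var(Y) = v and r = ρ√v / √(1 − ρ² + ρ²v).

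*Selection by worsening from baseline:* Y − X has variance 2(1 − ρ) = 0.8 and is independent of X + Y, which has variance 2(1 + ρ) = 3.2. Only the first shrinks, so Var(Y) = (3.2 + 0.8v)/4 and r = (3.2 − 0.8v)/(3.2 + 0.8v).

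The baseline-adjusted residual variance is SD²(1 − r²), with true value 1 − 0.36 = 0.64. Results use unrounded values:

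| Lost | Selected by | SD | r | Residual variance / 0.64 | Shortfall, that arm | Shortfall, mean of both arms if one affected |
|---|---|---|---|---|---|---|
| 5% | level | 0.90 | 0.56 | 0.87 | 13% | about 7% |
| 5% | change | 0.98 | 0.66 | 0.84 | 16% | about 8% |
| 10% | level | 0.84 | 0.53 | 0.79 | 21% | about 10% |
| 10% | change | 0.97 | 0.70 | 0.76 | 24% | about 12% |

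The last column is half the one before it, because the other arm is unaffected.

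**4. Sensitivity.** By simulation with ρ from 0.4 to 0.8, the affected arm's shortfall is 13 to 27% when the worst 10% are lost, and 6 to 13% when one family in 30 is lost. If follow-up continues after removal, this mechanism causes no bias.

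**5. Effect on a later trial.** Take an assumed standardised effect of 0.5, two-sided 5% level and 80% power, which needs 63 per arm.
- Variance understated by 10% (SD 0.95): 57 per arm and true power of 76%.
- Variance understated by 19% (SD 0.90): 51 per arm and true power of 71%.

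**6. Sampling error for comparison.** With 22 per arm, the 95% interval for an SD runs from √(21/35.48) = 0.77 to √(21/10.28) = 1.43 times the estimate. For an observed r of 0.6, the Fisher interval is 0.24 to 0.82.

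**The case against.** The strongest reply is that the section already deals with this. Worsening leads to a clinical assessment and a discretionary decision, not to automatic removal; the stated ground is that the study is doing harm. Collected data are kept. Withdrawn participants are encouraged to continue, a PI-initiated end to the intervention is provided for with follow-up intact, and the Premature Termination form records the reason and who decided. All of this stands, and it makes the bias conditional. It does not say what removal from the study means for the remaining assessments.

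Three stronger readings are tempting, and the documents do not support them.
- *Bad outcomes are deleted.* Nothing already collected is discarded. At most, later assessments are not obtained.
- *The correlation is inflated.* That holds under selection by change. Under selection by level it falls. The lowest SD (0.84) and the highest correlation (0.70) come from different mechanisms and cannot be combined. What holds under both is that the residual variance is too small.
- *PRE-CARE will look better.* Section 12.3 disclaims between-group comparison and effect estimation, so no planned analysis carries that error.

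It is also fair to say that detection is not exclusive to PRE-CARE. Treating providers may raise concerns, controls may contact staff, and both arms complete questionnaires. Sampling error at this size also exceeds the bias. That limits the practical weight of the point, but does not justify an avoidable error whose direction on the residual variance is known.

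**Conclusion.** The point holds as an unresolved conflict within one section. The removal paragraph permits removal from the study after worsening on a primary outcome or of parental symptoms, and neither withdrawal type covers it, so follow-up of worsening families may stop against the protocol's own intention-to-treat aim.

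If it does stop, the affected arm's baseline-adjusted residual variance is understated by 13 to 24%, or about 7 to 12% averaged over arms if only one is affected. This rests on normality, a true correlation of 0.6, and loss of exactly the worst 5 to 10%. Because the documents give no removal rate and real decisions would not pick out precisely the worst cases, it is an illustrative upper range, not a forecast. No view is taken on when a family ought to be removed. The passages need reconciling because doing so changes which data are collected, at almost no cost.

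**What to change.** Reconcile the removal paragraph with the two withdrawal definitions, leaving the removal decision with the PI. State, for both arms, that a PI removal does not by itself end the 3-, 6- and 12-month assessments. These are still offered unless the participant declines or the investigator documents that contact is inappropriate. The wording has to be about follow-up: equating removal with removal from the intervention would have no meaning for controls.

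Report PI removals by arm and reason. The Premature Termination form already captures the reason and the decision-maker, so only the tabulation by arm is new.

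The cost is a short protocol edit and a few questionnaires that are already scheduled and budgeted.

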### **Zoom Videoconferencing**

Participants will have the option to complete any parts of the intervention and study via Zoom Video Communications software. Zoom Video Communications is a remote conferencing services company that provides remote conferencing services, that combines video conferencing, screen sharing services, online meetings, chat, and mobile collaboration, with both audio and video communication options. We will use a BMC Zoom account which is HIPAA compliant. Participants can use zoom via their phone, computer, or tablet/Ipad. Intervention sessions will not be recorded. We will audio record only the final exit interview, with the permission of the participant, using a digital voice recorders or audio recording programs on our BMC encrypted study laptops. Participant’s video feed in zoom will not be recorded during

this process. Once the interview is complete, the audio will be saved and coded with the subject unique identifiers, only connected to identifiers (PHI) via a separate, password-protected, master code. The audio file will be saved directly from the audio recorder or audio recording program on a secure, password protected server at Boston Medical Center (BMC) to which only designated individuals have access, thus providing a secure environment for all project data.

It is vital for the research team to provide a remote videoconferencing option to participants receiving the intervention for public health reasons. This will not only enable research teams to continue conducting vital research work during pandemics such as COVID-19, but will also allow patients to receive psycho-social and educational interventions and health care services that counteract many logistical and financial barriers. This includes access to care barriers, including distance to health care facilities, financial burden of transportation to health care facilities, financial burden of arranging childcare, and health conditions/pandemics that may prevent patients from leaving their homes.

## 10 Assessment of Safety and Data Safety Monitoring Plan (DSMP)

### 10.1 Definitions

The following definitions will be used in the assessment of safety:

*Adverse Event (AE)* is defined as an event or group of events together that pose potential physical, emotional, legal or financial risk that is/are plausibly related to the research intervention and/or research procedures. Thus, AEs in this study could include any substantial or significant changes to the participant's mental health and symptoms, abnormal or harmful behaviors, suicidal behavior or attempts, or breach in the protection of participant data or breach of confidentiality because they are plausible in regards to our study intervention/procedures. We will document such AEs, whether or not considered related to the participants' participation in the research. The investigator or designee will make a determination regarding relatedness to the study intervention and/or procedures. We will not track physical signs and symptoms, abnormal lab results, new diagnoses, etc. as AEs.

*Serious Adverse Event (SAE)* is any adverse event that

- (1) results in death;
- (2) is life-threatening;
- (3) results in inpatient hospitalization or prolongation of existing hospitalization;
- (4) results in a persistent or significant disability/incapacity;
- (5) results in a congenital anomaly/birth defect; or
- (6) based upon appropriate medical judgment, may jeopardize the subject's health and well-being and requires hospitalization, other mental health or medical stabilization, child protection services or other higher level of care

*Life-threatening* means that the event places the subject at immediate risk of death from the event as it occurred.

*Unanticipated Problem* is defined as an event, experience or outcome that meets **all three** of the following criteria:

- is unexpected; AND
- is related or possibly related to participation in the research; AND
- suggests that the research places subjects or others at a greater risk of harm (including physical, psychological, economic, or social harm) than was previously known or recognized.

*Possibly related* means there is a reasonable possibility that the incident, experience, or outcome may have been caused by the procedures involved in the research

*Unexpected* means the nature, severity, or frequency of the event is not consistent with either:

- the known or foreseeable risk of adverse events associated with the procedures involved in the research that are described in (a) the protocol-related documents, such as the IRB-approved research protocol, any applicable investigator brochure, and the current IRB-approved informed consent document, and (b) other relevant sources of information, such as product labeling and package inserts; or
- the expected natural progression of any underlying disease, disorder, or condition of the subject(s) experiencing the adverse event and the subject's predisposing risk factor profile for the adverse event.

## 10.2 Safety Review

The Principal Investigator will be ultimately responsible for the overall conduct of the study including ensuring that any Adverse Events are recorded and reported according to BUMC IRB policy. If adverse events, unanticipated problems or study deviations arise, then the academic institution's Institutional Review Board (IRB) will be notified using an Adverse Event Form. If the adverse event is an unanticipated problem, it will be reported to the IRB within 7 days of its identification. The principal investigator will also report the findings to the NIH program staff. The NIH will be informed of any actions taken by the IRB as a result of their continuing review.

Security or inadvertent confidentiality breaches as well as suspected child maltreatment or other events that require mandated reporting will be recorded as adverse events. The study team has a detailed safety protocol in place to address child maltreatment, mental health emergencies, and other related safety concerns as they arise. We will continually monitor whether and how often the protocols are needed and, once activated, if they function as expected. If they do not, that will also be considered an adverse event and will be assessed as an unanticipated problem. No other Adverse Events/Serious Adverse Events are anticipated – any that arise and meet the definition of an unanticipated problem will be reported to the IRB in compliance with the IRB reporting policies.

**Data Safety Monitoring Board**

In addition, because this project includes an intervention intended to impact clinical outcomes, the inclusion of a Data and Safety Monitoring Plan and Board is appropriate. The Data and Safety Monitoring Board (DSMB) will include an independent group of experts on child behavioral health, clinical trials, and biostatistics, who will advise and monitor the project with the study principal investigator (PI). None of the members will directly supervise, report to, or directly collaborate with the PI. The following three members will serve on the DSMB:

- 1) **[name] [name]**, Assistant Professor in Department of Child and Adolescent Psychiatry, Johns Hopkins University/Johns Hopkins Bayview Medical Center
- 2) **[name]**, Vice Chair for Research in Pediatrics, University of Massachusetts Medical School
- 3) **[name] [name]**, Research Associate Professor of Health Law, Policy, and Management at the Boston University School of Public Health

The DSMB will meet every six months (+/- 30 days for flexible scheduling). Its primary responsibilities will be to:

- 1) Review and evaluate the accumulated study data for participant safety, study conduct and progress, and efficacy; and
- 2) Make recommendations concerning the continuation, modification, or termination of the trial.

In this proposed project, the DSMB will consider study-specific data and any concerns for poor clinical outcomes among patients in a particular randomization condition. As part of their responsibility, DSMB members will ensure the timeliness, completeness, and accuracy of the data submitted to them for review. Members will ensure submitted data are sufficient for evaluation of the safety and welfare of study participants. The DSMB will also assess the performance of overall study operations and any other relevant issues, as necessary.

Specific items to be reviewed by the DSMB will include:

- Interim/cumulative data for evidence of study-related adverse events;
- Interim/cumulative data for evidence of efficacy according to pre-established statistical guidelines;
- Data quality, completeness, and timeliness;
- Adequacy of compliance with goals for recruitment and retention, including those related to the participation of women and minorities;
- Adherence to the protocol;
- Factors that might affect the study outcome or compromise the confidentiality of the trial data; and
- Factors external to the study such as scientific or therapeutic developments that may impact participant safety or the ethics of the study.

After each meeting of the DSMB, members will meet without the study PIs and provide them with a written letter of recommendations.

### 10.3 Reporting Plans

The Principal Investigator at BMC/BU Medical Campus will report Unanticipated Problems, safety monitors' reports, and Adverse Events to the BMC/BU Medical Center IRB in accordance with IRB policies:

- Unanticipated Problems occurring at BMC/BU Medical Campus will be reported to the IRB within 7 days of the investigator learning of the event.
- Reports from safety monitors with recommended changes will be reported to the IRB within 7 days of the investigator receiving the report.
- Adverse Events (including Serious Adverse Events) will be reported in summary at the time of continuing review, along with a statement that the pattern of adverse events, in total, does not suggest that the research places subjects or others at a greater risk of harm than was previously known.
- Reports from safety monitors with no recommended changes will be reported to the IRB at the time of continuing review.

